procedures provided to subjects in the ACP intervention and attention-control groups will be reviewed by an independent research staff every 3 months to check the extent to which they are consistent with the group protocol. To this end, the research staff will interview randomly selected patient-caregiver dyads in each study group. Third, the workbook and video will be created systematically, starting with a review of the ACP literature in advanced cancer. The workbook content and overall video design will be reviewed for appropriateness and accuracy by 2 physicians specializing in cancer care, 1 ICU physician, 1 expert in palliative medicine, and 1 nurse with expertise in clinical decision-making.

Data collection procedures: Assessments will be performed prospectively and continue until patient death, loss to follow-up, study withdrawal, or when the patient can no longer be interviewed. An every-3-week time frame will be used in this study for repeated QOL and other outcomes assessments for both patients and their family caregivers bases on the review of literature to cover the most rapid change of patient physical conditions and demanding period of caregiving until the death of the patient. After each patient's death, a chart review and postmortem interview with patients' caregivers will be performed to confirm the type of medical care received at the EOL. Bereavement interviews will be conducted 1, 3, 6 and 13 months after the time of death in order to avoid contamination on the basis of anniversary grief reactions.

Data safety and management plan

An independent Data and Safety Monitoring Board (DSMB) will be organized to ensure patient safety throughout the trial as well as its validity and scientific merits. The DSMB will comprise a biostatistician experienced in statistical methods for clinical trials, a nursing researcher experienced in conducting randomized controlled trials, and a physician-scientist experienced in cancer care. The DSMB will monitor and address the following issues: (1) sufficient and appropriate enrollment of subjects, including compliance with the eligibility criteria for each dyad of terminally ill cancer patients and family caregivers, (2) appropriate

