The effectiveness of the intervention will be examined using intention-to-treat analyses with generalized estimating equations (GEE) or hierarchical generalized linear modeling (HGLM). Effectiveness of the intervention will be assessed in terms of (1) facilitating prognostic awareness, EOL care discussions, patient-caregiver agreement on preferences for EOL care, and congruence between patients' preferred and actual EOL care, (2) improving patients' and family caregivers' QOL, anxiety and depressive symptoms before the patient's death, and family caregiver bereavement outcomes, and (3) limiting aggressive healthcare resource utilization at EOL. In the intention-to-treat analyses, all participants will be analyzed in the study group to which they are initially allocated, regardless of whether they complete or withdraw from the study. The GEE/HGLM uses robust standard error estimates to take into account (1) within-subject correlations of the outcome variables during the study period, (2) unequal numbers of assessments among subjects, and (3) potential missing observations. In GEE/HGLM analysis, incompleteness of the outcome variables has only marginal influence on the results of longitudinal data analysis because GEE/HGLM involves fitting a generalized linear model to the marginal distribution of repeated outcomes.¹⁵¹

The congruence between terminally ill cancer patients' preferred and actual EOL care will be determined by comparing the agreement between preferences for EOL care elicited at the last assessment and actual EOL care. Preferences for each EOL care treatment will be dichotomized so that those who are "unsure" whether prefer a specific EOL care treatment will be counted as desiring that treatment because in most instances the clinical default is to provide

treatment unless specifically refused.⁷² In addition to the percentage of overall agreement, kappa coefficients will be computed to correct for the amount of agreement that can be expected by chance alone.¹⁵²

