Subsequently, multivariate logistic regression with the GEE method will be used to examine the impact of the ACP intervention on improving the congruence between patients' preferred and actual EOL care, and on secondary outcomes--increasing prognostic awareness, EOL care discussions, and patient-caregiver agreement on preferences for EOL care, and decreasing aggressive healthcare resource utilization at EOL, with simultaneous adjustment for time-varying and invariant confounding factors. The GEE model will also be used to examine the moderation effects of prognostic awareness, EOL care discussions, and patient-caregiver agreement on preferences for EOL care on the ACP intervention's effectiveness in increasing the congruence between patients' preferred and actual EOL care and in decreasing aggressive healthcare resource utilization at EOL.

Multivariate multiple regression with the GEE/HGLM method will be used to test the effectiveness of the ACP intervention in improving patients' and family caregivers' QOL and psychological well-being (depressive and anxiety symptoms) before the patient's death, and family caregiver bereavement outcomes (including QOL, depressive symptoms, and grief reactions), with simultaneous adjustment for time-varying and invariant confounding factors. The GEE/HGLM model will also be used to examine the moderation effects of prognostic awareness, EOL care discussions, patient-caregiver agreement on preferences for EOL care, aggressive healthcare resource utilization, and the extent of congruence between patients' preferred and actual EOL care on the ACP intervention's effectiveness in improving patients' and caregivers' QOL, anxiety and depressive symptoms before the patient's death and facilitating family caregiver bereavement adjustment.

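### Two of the five planned moderators of the ACP effect have no pre-allocation version, and the other three are not limited to theirs

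*Combined protocol and SAP*

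**What the plan says.** The Statistical analysis plan contains two moderation sentences.

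- For congruence and aggressive care as outcomes: "The GEE model will also be used to examine the moderation effects of prognostic awareness, EOL care discussions, and patient-caregiver agreement". This set has three moderators.
- For patients' and caregivers' quality of life and mood before death, and for caregiver bereavement: "moderation effects of prognostic awareness, EOL care discussions, patient-caregiver agreement on preferences for EOL care, aggressive healthcare resource utilization, and the extent of congruence". This set has the same three plus two more.

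The same section names all five as measures of effectiveness: "facilitating prognostic awareness, EOL care discussions, patient-caregiver agreement on preferences for EOL care, and congruence between patients' preferred and actual EOL care", and "limiting aggressive healthcare resource utilization at EOL". It later calls four of them "secondary outcomes--increasing prognostic awareness, EOL care discussions, and patient-caregiver agreement on preferences for EOL care, and decreasing aggressive healthcare resource utilization", and the Specific Aims make congruence a primary objective. The models are to be fitted "with simultaneous adjustment for time-varying and invariant confounding factors", but the section does not list those factors.

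Congruence is obtained by "comparing the agreement between preferences for EOL care elicited at the last assessment and actual EOL care". Under Data collection procedures, after the patient dies, "a chart review and postmortem interview with patients' caregivers will be performed to confirm the type of medical care received at the EOL".

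Nothing limits any moderator to a value recorded before allocation.

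**The concern.** A moderator of a randomised effect should be fixed before allocation, so that each of its levels contains two comparable randomised groups. If allocation itself changes the variable, patients at a given level in the ACP arm got there by a different route from those at the same level in the control arm. Randomisation no longer makes them comparable.

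What is at stake is the reading of these additional analyses. A statement that ACP works better in patients who had a discussion, or who received care matching their wishes, could reflect who ended up in those groups rather than what ACP did. For congruence there is also a problem of time order: it is settled only by care near death, yet it is meant to moderate effects on quality of life and mood recorded every three weeks before then.

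**Working it through.** **Step 1: compare the text.** The plan gives no figure to reproduce.

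- Moderators also named as outcomes: 5 of 5. Moderators limited to baseline: 0 of 5.
- Congruence needs the last stated preference and the care actually received, so no value exists at enrolment. Aggressive utilisation is defined as care at the end of life, so it has none either.
- For awareness, discussions and dyad agreement, a pre-allocation value should exist. Under Randomization the envelope is opened only after the initial assessment, and the Statistical analysis plan compares baseline outcomes between groups. Neither place itemises the three.
- For bereavement, congruence and utilisation come first in time but are still affected by allocation.

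**Step 2: illustrate the size.** From the documents: 231 per arm and 18.5% attrition, so 231 × 0.815 = 188 per arm; and the odds ratio of 2.26 between discussion and congruence (Sample size calculation). Everything else is assumed:

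- no true ACP effect, and congruence 50% in both arms;
- discussions in 30 vs 45%, 30 vs 60% or 20 vs 70% (control vs ACP);
- one unadjusted normal trait U, with strength s in log-odds per SD for both discussion and congruence;
- f, the trait-discussion link in the ACP arm relative to control.

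Model: P(discussion) = expit(a + f·s·U), with f = 1 in control and a set to give the stated rate; P(congruence) = expit(s·U). Congruence among those with a discussion is E[expit(sU)·P(discussion)] / E[P(discussion)], and likewise for those without. The level odds ratio is the ACP odds over the control odds.

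Example with s = 0.8, f = 1, 30 vs 60%. Congruence without and with discussion is 0.462 and 0.588 in control, and 0.425 and 0.550 under ACP.

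- Overall, control: 0.7 × 0.462 + 0.3 × 0.588 = 0.50. ACP: 0.4 × 0.425 + 0.6 × 0.550 = 0.50.
- No discussion: (0.425/0.575)/(0.462/0.538) = 0.86. Discussion: (0.550/0.450)/(0.588/0.412) = 0.86.

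The arms are equal overall, yet ACP looks worse at both levels.

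Ranges over the three discussion scenarios (20,000 simulated trials each, two-sided 5% Wald tests):

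| s | Interaction, equal link | Link halved | Link removed | Level ORs, equal link | Any level significant, equal link |
|---|---|---|---|---|---|
| 0.4 | 4.7–5.0% | 5.2–5.4% | 5.9–6.4% | 0.93–0.98 | 9.8–10.7% |
| 0.8 | 4.7–5.0% | 8.1–8.2% | 18.4–21.3% | 0.77–0.93 | 10.7–20.7% |
| 1.0 | 4.9–5.1% | 10.5–11.3% | 31.3–37.1% | 0.69–0.90 | 12.0–32.3% |

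With no trait, at least one level is significant in 9.3–9.9% of trials; two independent 5% tests give 1 − 0.95² = 9.75%.

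**Step 3: bound the trait.** The trait alone would imply a discussion-congruence odds ratio of 1.16 (s = 0.4), 1.65–1.67 (0.8) or 2.02–2.08 (1.0). As a share of ln 2.26 = 0.815 that is 18%, 61–63% or 86–90%. Strengths of 0.8 to 1.0 are therefore pessimistic.

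**Step 4: allow for adjustment.** Half the trait variance was taken as a measured covariate, for s = 0.8–1.0 in the 30 vs 60% and 20 vs 70% scenarios only (4,000 trials each). In those same scenarios, interaction rejection falls from 8.1–10.9% to 6.1–7.0% (link halved) and from 18.4–36.2% to 9.2–14.1% (link removed). Level odds ratios with an equal link move from 0.69–0.86 to 0.79–0.92.

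**Step 5: congruence as moderator of pre-death quality of life.** Assumed: congruence 50% vs 69%, trait-QOL correlation 0.3–0.5, one value per patient, no QOL effect (10,000 trials). Interaction rejection is 5.0–5.4% with an equal link and 5.9–12.2% with the link halved. Level differences with an equal link are −0.02 to −0.08 SD.

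**The case against.** Moderation normally implies baseline variables, and for three of the five that reading is open. For those three the fault is under-specification, not a demonstrated error. This stands. It does not rescue the list as a whole, because congruence appears in the same sentence and cannot be measured at baseline.

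The natural test of moderation is the interaction, and it holds its level unless two assumptions are combined: a strong trait, and ACP weakening its link with the moderator. The within-level readings, where drift appears even with an equal link, are not named in the plan. The plan also intends confounder adjustment, and it analyses repeated measures where the simulations use one outcome per patient. All of this stands, and it means the simulations show that bias is possible, not that it is likely or large. Some weakening of the link is plausible, since the ACP arm actively prompts discussions while the control arm leaves them to usual practice, but the documents give no measure of it. Adjustment by unnamed factors cannot be relied on to remove the selection.

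No time window is given for aggressive utilisation, and the ACP Intervention section shows that intensive care can occur during follow-up. Some utilisation might therefore precede a later quality-of-life visit. That section lists triggers for a further intervention course, however; it does not define the outcome. Care received after allocation is in any case open to influence by ACP.

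A reader might infer that all five moderators are invalid in the same way, that the false-positive rate will be near 37%, or that the trial's main conclusions are compromised. The documents support none of these. Three moderators have a usable baseline form. The 37.1% needs the strongest trait, complete removal of the link and no adjustment. The main comparisons involve no moderator.

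**Conclusion.** The concern holds in a limited form. It is definite for congruence and end-of-life utilisation, which are used only in the second moderation sentence. For awareness, discussions and dyad agreement, used in both sentences, it is a gap in specification.

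The conclusion rests on the definitions in the plan and does not depend on the simulations. Even where the interaction test keeps its nominal level, a contrast across groups that ACP helped to form has no randomised interpretation. How large the distortion would be cannot be known from the documents, because the trait strengths, discussion rates and link changes are all assumed.

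The intention-to-treat comparisons, the primary objectives and the sample size are untouched. The point should be addressed before analysis, but it is confined to these additional analyses.

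**What to change.** In both moderation sentences of the Statistical analysis plan, define awareness of prognosis, discussion status and dyad agreement by their values at the initial assessment before allocation, and test each as an ACP-by-moderator interaction. Remove congruence and end-of-life utilisation as moderators.

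Label any analysis of post-randomisation versions exploratory and associational. If it is framed as mediation, it must respect time order and use a method that allows for confounders themselves affected by ACP, with its assumptions stated. Stating that there is no unmeasured confounding is not enough: awareness, discussions and agreement are meant to be changed by ACP and may in turn influence congruence and utilisation.

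The cost is SAP wording, provided the initial assessment records the three items, which should be confirmed. The downside is power: baseline moderators may vary little, for example if few dyads have had a discussion before enrolment, so the interaction tests may be weak.
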